		scheduled treatment date. Study drug/study regimen can be resumed at the next scheduled dose once event stabilizes to grade ≤1 or baseline and at least 5 days have passed after completion of steroid taper.	If event is persistent (>5 days) or worsens, promptly start prednisone 1- 2mg/kg/day or IV equivalent. If still no improvement within 5 days despite 1-2mg/kg/day of prednisone or IV equivalent, consider additional workup and prompt treatment with IV methylprednisolone 2-4mg/kg/day or equivalent. If still no improvement within 5 days despite 2-4mg/kg/day of IV methylprednisolone or equivalent, promptly start immunosuppressives (mycophenolate mofetil ¹ or equivalent). Infliximab should NOT be used. Once improving, gradually taper steroids over ≥28 days and consider prophylactic antibiotics, antifungals and anti PCP treatment (please refer to current NCCN guidelines for treatment of cancer-related infections [Category 2B recommendation]) ⁴⁵ .
	Grade 3	For elevations in transaminases $\leq 8 \times$ ULN, or elevations in bilirubin $\leq 5 \times$ ULN:	Promptly initiate empiric IV methylprednisolone at 1 to 4 mg/kg/day or equivalent.
		Hold study drug/study regimen	If still no improvement within 5 days despite 1 to 4 mg/kg/day methylprednisolone IV or equivalent,

Table 3: Dos	ing Modifie	cation and Toxicity Manag mediated Adverse F	ement Guidelines for Specific Immune- Reactions
Toxicity	Grade of the Event (NCI CTCAE version 4.03)	Dose Modifications	Toxicity Management

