		dose until resolution to \leq Grade 1 or baseline • Resume study drug/study regimen administration at the next scheduled dose if elevations downgrade \leq Grade 1 or baseline within 14 days Permanently discontinue study drug/study regimen if the elevations do not downgrade to \leq Grade 1 or baseline within 14 days. For elevations in transaminases > 8 × ULN or elevations in bilirubin > 5 × ULN, discontinue study drug/study regimen. Permanently discontinue study drug/study regimen for any case meeting Hy's law criteria (ALT > 3x ULN + bilirubin > 2x ULN without initial findings of cholestasis [i.e. elevated alkaline PO4] and in the absence of any alternative cause ⁴⁶).	promptly start treatment with immunosuppressive therapy (mycophenolate mofetil or equivalent). Infliximab should NOT be used. Consider hepatology consult, abdominal work-up, and imaging as appropriate. Once improving, gradually taper steroids over ≥28 days and consider prophylactic antibiotics, antifungals and anti PCP treatment (please refer to current NCCN guidelines for treatment of cancer-related infections [Category 2B recommendation]) ⁴⁵ .

Table 3: Dos	sing Modifi	ing Modification and Toxicity Management Guidelines for Specific Immune mediated Adverse Reactions		
Toxicity	Grade of the Event (NCI CTCAE version 4.03)	Dose Modifications	Toxicity Management	
	Grade 4	Permanently discontinue study drug/study regimen.	Promptly initiate empiric IV methylprednisolone at 1 to 4 mg/kg/day or equivalent.	
			If still no improvement within 5 days despite 1 to 4 mg/kg/day methylprednisolone IV or equivalent, promptly start treatment with immunosuppressive therapy (mycophenolate mofetil or equivalent). Infliximab should NOT be used.	
			Consider hepatology consult, abdominal work-up, and imaging as appropriate.	
			Once improving, gradually taper steroids over ≥28 days and consider prophylactic antibiotics, antifungals and anti PCP treatment (please refer to current NCCN guidelines for treatment of cancer-related infections [Category 2B recommendation]) ⁴⁵ .	
Nephritis or Renal Dysfunction (Elevated		tions of serum creatinine of gist as clinically appropriate	any grade, consider consulting with a	
Serum Creatinine)	function	(e.g. elevated serum BUN ar	may be related to changes in renal nd creatinine, decreased creatinine crease in urine output, proteinuria, etc.).	
		hould be thoroughly evaluate ease progression, infections	ted to rule out any alternative etiology etc.).	

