	Grade 3 Grade 4	Hold study drug/study regimen until resolution to ≤ Grade 1 or baseline. If temporarily holding the study drug/study regimen does not provide improvement of the Grade 3 skin rash to ≤ Grade 1 or baseline within 30 days, then permanently discontinue study drug/study regimen. Permanently discontinue study drug/study regimen	 Consult dermatology as clinically indicated. Promptly initiate empiric IV methylprednisolone 1 to 4 mg/kg/day or equivalent. Consider hospitalization if clinically indicated. Consider skin biopsy (preferably more than 1) as clinically feasible. Once improving, gradually taper steroids over ≥28 days and consider prophylactic antibiotics, antifungals
		study drug/study regimen	and anti PCP treatment (please refer to current NCCN guidelines for treatment of cancer-related infections [Category 2B recommendation]) ⁴⁵ .

Toxicity	Grade of the Event (NCI CTCAE version 4.03)	Dose Modifications	Toxicity Management
	,		Discuss with Overall PI.
Endocrinopathy		nts experiencing endocrinop ndocrinologist as clinically a	athy of any grade, consider consulting appropriate.
(e.g., hyperthyroidism, hypothyroidism, hypopituitarism, adrenal insufficiency, etc.)	endocrino changes, c hypotensi Patients sl (e.g., dise Monitor a	pathies. Non-specific symp changed mental status, verti on and weakness. hould be thoroughly evaluat ase progression including b nd evaluate thyroid function	ents for signs and symptoms of ptoms include headache, fatigue, behavior go, abdominal pain, unusual bowel habits, ted to rule out any alternative etiology rain metastases, infections, etc.) n tests: TSH, free T3 and free T4 and other
	If a patien autoimmu insipidus)	ine nature (e.g., thyroiditis,	suspected endocrinopathy. grade that is thought to be possibly of pancreatitis, hypophysitis, diabetes and a blood sample for appropriate
	Grade 1 (including those with asymptom -atic TSH elevation)	No dose delay.	Monitor patient with appropriate endocrine function tests. If TSH < 0.5X LLN, or TSH >2X ULN or consistently out of range in 2 subsequent measurements, include FT4 at subsequent cycles as clinically indicated and consider endocrinology consult.
	Grade 2	For endocrinopathy other than hypothyroidism, hold study drug/study regimen dose until subject is	Initiate hormone replacement as needed for management. Evaluate endocrine function, and as clinically indicated, consider pituitary scan.

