	If symptoms recur or worsen during corticosteroid tapering (<28 days of taper), increase the corticosteroid dose until stabilization or improvement of symptoms, then resume corticosteroid tapering at a			
		can be resumed at the next scheduled dose once event stabilizes to grade ≤1 or baseline and at least 5 days have passed after completion of steroid taper. Patients with endocrinopathies who may require prolonged or continued steroid	slower rate (≥ 28 days of taper) More potent immunosuppressives such as TNF inhibitors (e.g. infliximab) should be considered for events not responding to systemic steroids (also refer to the individual sections of the immune related adverse event for specific type of immunosuppressive).	

Table 4: Tox	Table 4: Toxicity Management Guidelines for Immune-related Adverse Events no Noted			
Adverse Event		Dose Modifications	Toxicity Guidance	
Event	Grade 3	 replacement can be retreated with study drug/study regimen on the following conditions: 1) The event stabilizes and is controlled 2) The patient is clinically stable as per treating physician's clinical judgment 3) Doses of prednisone are at less than or equal to 10mg/day or equivalent. Hold study drug/study regimen until resolution to ≤ Grade 1 or baseline. For Grade 3 and above asymptomatic amylase or lipase levels hold study drug/regimen. If complete work up shows no evidence of pancreatitis, may continue or resume study drug/regimen. Study drug/study regimen can be resumed at the next scheduled dose once event stabilizes to grade ≤ 1 or baseline and at least 5 days have passed after completion of steroid taper. 	Note: Discontinuation of study drug is not mandated for Grade 3 / Grade 4 inflammatory reactions attributed to local tumour response (e.g. inflammatory reaction at sites of metastatic disease, lymph nodes etc.). Continuation of study drug in this situation should be based upon a benefit/risk analysis for that patient made by the treating investigator.	
	Grade 4	Permanently discontinue study drug/study regimen. For Grade 3 and above		

Table 4: Toxicity Management Guidelines for Immune-related Adverse Events not Otherwise Noted			
Adverse Event	Dose Modifications	Toxicity Guidance	
	asymptomatic amylase or lipase levels hold study drug/regimen and if complete work up shows no evidence of pancreatitis, may continue or resume study drug/regimen.		

Table :	Table 5: Dosing Modification and Toxicity Management Guidelines for Infusion-Related Reactions			

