Severity Grade	Dose Modifications Toxicity Management			
0	ent of any infusion-related reaction of the treating investigator.	n should be per institutional standard at the		
chills, flush discomfort,	ing and/or itching, alterations in hea	infusion-related reactions (e.g., fever and/or shaking art rate and blood pressure, dyspnea or chest .g., generalized urticaria, angioedema, wheezing,		
Grade 1	The infusion rate of study	For Grade 1 or Grade 2:		
	drug/study regimen may be decreased by 50% or temporarily interrupted until resolution of the event.	Acetaminophen and/or antihistamines may be administered per institutional standard at the discretion of the investigator.		
Grade 2	The infusion rate of study drug/study regimen may be decreased 50% or temporarily interrupted until resolution of the event.	Consider premedication per institutional standard prior to subsequent doses.		
	Subsequent infusions may be given at 50% of the initial infusion rate.			
Grade ≥ 3	Permanently discontinue study drug/study regimen.	Manage severe infusion-related reactions per institutional standards (e.g., IM epinephrine, followed by IV diphenhydramine and ranitidine, and IV glucocorticoid).		

Table 6: Dosing Modification and Toxicity Management Guidelines for Non-Immune		
Mediated Reactions		

СТС	Dose Modification	Toxicity Management	
Grade/Severity		Tomory Frangement	
Note: dose delays are not required for adverse events not deemed to be related to study treatment (i.e. events due to underlying disease) or for laboratory abnormalities not deemed to be clinically significant. At the treating investigator's discretion, study medication dosing may be held for toxicity considered unlikely related or unrelated to study treatment. In the event of a dosing delay for unrelated adverse events, the maximum amount of time either study medication may be held is 28 days.			
Grade 1	No dose adjustment	Treat accordingly as per institutional standard.	
Grade 2	At the treating investigator's discretion, study drug/regimen may be held until resolution to \leq Grade 1 or baseline.	Treat accordingly as per institutional standard	
Grade 3	Hold study drug/study regimen until resolution to \leq Grade 1 or baseline.	Treat accordingly as per institutional standard	
	For AEs that downgrade to \leq Grade 2 within 7 days or resolve to \leq Grade 1 or baseline within 14 days, resume study drug/study regimen administration at next scheduled dose. Otherwise, discontinue study drug/study regimen.		

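### The hold and discontinue bands for Grade 3 hepatitis in Table 3 overlap, and Table 6 leaves the Grade 3 restart level unclear

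*Combined protocol and SAP*

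**What the plan says.** **Table 3, hepatitis, Grade 3.** The hold line opens "For elevations in transaminases $\leq 8 \times$ ULN, or elevations in bilirubin $\leq 5 \times$ ULN". Under it, dosing may restart at the next scheduled dose if the tests settle to Grade 1 or baseline within 14 days; if they do not, treatment stops for good. The next line reads "For elevations in transaminases > 8 × ULN or elevations in bilirubin > 5 × ULN, discontinue study drug/study regimen". A separate Hy's law rule ends treatment when ALT exceeds 3 x ULN and bilirubin exceeds 2 x ULN, provided there is no initial cholestasis and no other cause. No sentence ranks the hold line against the discontinue line.

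**Table 6, Grade 3 (non-immune reactions).** Sentence 1 is "Hold study drug/study regimen until resolution to \leq Grade 1 or baseline". Sentence 2 begins "For AEs that downgrade to \leq Grade 2 within 7 days", adds a second route (Grade 1 or baseline within 14 days), and ends "resume study drug/study regimen administration at next scheduled dose. Otherwise, discontinue study drug/study regimen". The Grade 2 row of the same table leaves holding to the investigator: "study drug/regimen may be held until resolution to \leq Grade 1 or baseline".

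Section 6 makes these tables the operative dosing rules. It bars dose reductions, and it does not allow tremelimumab to be reinstated once it has been stopped early for toxicity.

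**The concern.** A stop or restart rule should give one answer for each patient. In the hepatitis row, two sites could treat the same liver tests differently: one holds and may re-dose within 14 days, the other ends treatment. In Table 6, one site doses a patient whose event is still Grade 2 on the dosing day, and another holds.

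An error in either direction matters. Re-dosing is at full dose, because reductions are not allowed. Stopping without need costs the patient the remaining therapy. What is at stake is patient safety and consistent dosing. The test of the response rate is not involved.

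**Working it through.** No figure in the plan needs reproducing here; the check is one of logic.

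**Hepatitis Grade 3.** Let T be transaminases (ALT and AST taken as equal) and B bilirubin, both in multiples of ULN.

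- Hold line: T ≤ 8 or B ≤ 5.
- Discontinue line: T > 8 or B > 5.
- The exact opposite of the discontinue line is T ≤ 8 **and** B ≤ 5. The hold line uses 'or', so it is wider than that opposite, and the excess is the overlap.

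Each band is applied only to a test that is itself at Grade 3 level. The protocol does not print the CTCAE cut-offs. I assume that the values below count as Grade 3 (6 to 10 for T, 4 to 6 for B), because the Grade 3 row itself splits at 8 and 5.

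| T | B | Cholestasis | Hold line | Discontinue line | Hy's law stop |
|---|---|---|---|---|---|
| 6 | not raised | – | yes | no | no |
| 10 | not raised | – | no | yes | no |
| not raised | 4 | – | yes | no | no |
| not raised | 6 | – | no | yes | no |
| 9 | 4.5 | yes | **yes** | **yes** | no |
| 7 | 6 | yes | **yes** | **yes** | no |
| 9 | 4.5 | no, and no other cause | yes | yes | yes (settles it) |
| 7 | 4 | yes | yes | no | no |

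With one raised test the bands do not overlap. With both raised and on opposite sides of their limits, both lines apply. The Hy's law stop settles such a case only when cholestasis and other causes are absent. With 'and' in the hold band, the 9 / 4.5 and 7 / 6 cases become discontinue only, 7 / 4 stays hold only, and no pair of values meets both lines.

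**Table 6 Grade 3.** Take every course in which the grade never rises, recorded at day 7, day 14 and the dosing day, with 1 standing for Grade 1 or lower or baseline. There are ten.

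- Four agree (both sentences resume): 3-1-1, 2-2-1, 2-1-1, 1-1-1.
- In five (3-3-3, 3-3-2, 3-3-1, 3-2-2, 3-2-1), sentence 2 discontinues while sentence 1 holds or resumes. These are coherent if sentence 2 is read as a time limit on the hold.
- In one (2-2-2), sentence 1 holds and sentence 2 doses.

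Example of the last, in a 28-day cycle: a Grade 3 event starts on day 10, is Grade 2 on day 16 (16 − 10 = 6 days, inside the 7), and is still Grade 2 on day 29, the next dosing day. Sentence 1 says hold; sentence 2 says dose.

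**The case against.** **Table 6.** The specific second sentence naturally qualifies the general first one: it names Grade 2 within 7 days, directs resumption, and closes with an 'otherwise'. The Grade 2 row supports this. A compulsory hold to Grade 1 would treat a downgraded event more strictly than one that began at Grade 2. This stands. A reader might infer two irreconcilable orders, but the text does not support that; what is missing is a linking word. The rash row keeps a single level throughout (drug stops if holding "does not provide improvement of the Grade 3 skin rash to ≤ Grade 1 or baseline within 30 days, then permanently discontinue"), but it covers an immune-mediated event, where a stricter rule is unsurprising, so the contrast proves little.

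The reach of the cell is also small. The note to Table 6 requires no delay for events judged unrelated to treatment or for laboratory changes judged not clinically significant. Table 4 treats events without a clear alternative cause as potentially immune-related. This stands too.

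**Hepatitis.** The discontinue line is unconditional, Table 4 refers back to the criteria for permanent discontinuation in Table 3, and a cautious reader would let the stop prevail. That is probably the intent. But the hold line is equally unconditional, no order of precedence is given, and the hold line leads to re-dosing.

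A reader might go further and count any bilirubin above ULN as an elevation, so that transaminases 10 x with bilirubin 1.8 x ULN would also meet both lines. The documents do not support this. The bands sit in the Grade 3 row, the Grade 1 hepatitis row requires no delay, and Section 3.1.8 admits patients with bilirubin up to 1.5 x ULN. With each band applied only to a Grade 3 test, that case is discontinue only.

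**Conclusion.** The hepatitis Grade 3 row is wrong as written, and the Table 6 Grade 3 cell is ambiguous. Both are minor.

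The hepatitis overlap is certain in logic but narrow. It needs both tests at Grade 3 level, exactly one above its limit, and a case outside the Hy's law stop. It rests on the assumption that values on either side of 8 x and 5 x ULN can both be Grade 3, which the row itself implies. The Table 6 problem is confined to an event that reaches Grade 2 within 7 days and is still Grade 2 on the dosing day.

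Few patients should be affected, but the documents give no count for either. A reader might try to derive a ceiling from the related Grade 3 or higher events among the 102 combination subjects in Section 2.4.2. That list omits events seen in a single subject, some events were uncoded at the cut-off, and it does not report transaminases and bilirubin jointly, so no ceiling follows.

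A reader might also see a contradiction between the ALT-only Hy's law stop in Table 3 and the ALT-or-AST definition in Section 7.9.2. The first is a dosing rule and the second a reporting definition, so they do not conflict.

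The consequences are for dosing safety and consistency only. Sample size, error rates and the response decision rule are unchanged.

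**What to change.** 1. **Table 3, hepatitis, Grade 3:** change the hold band to transaminases ≤ 8 x ULN **and** bilirubin ≤ 5 x ULN, and leave the discontinue band as it is. Exceeding either limit then means discontinue.
2. **Table 6, Grade 3:** reword sentence 1 so that drug is held to Grade 1 or baseline except where the event has fallen to Grade 2 or lower within 7 days, in which case dosing resumes at the next scheduled dose. If the sponsor does want Grade 1 or baseline on the dosing day, the 7-day clause should be deleted instead.

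The cost is rewording two table cells. No assessment, sample size or analysis changes.

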6.2 Overdose

There are no known antidotes for over-dosage of tremelimumab or durvalumab. In the case of suspected overdose, monitor hematologic parameters, serum chemistries, vital signs, cardiac and pulmonary function, and provide supportive care as necessary. See reporting requirements in

Section 7.9.

7. ADVERSE EVENTS: LIST AND REPORTING REQUIREMENTS

Adverse event (AE) monitoring and reporting is a routine part of every clinical trial. The following list of reported and/or potential AEs (Section 7.1) and the characteristics of an observed AE (Sections 7.3, 7.4, 7.5, and 7.10) will determine whether the event requires expedited reporting in addition to routine reporting.

7.1 Expected Toxicities

7.1.1 Adverse Event List for Durvalumab

Potential risks, based on the mechanism of action of durvalumab and related molecules, include immune-mediated reactions, such as colitis, pneumonitis, hepatitis/hepatotoxicity (elevations in ALT, AST, ALP, and/or total bilirubin), neuropathy/neuromuscular toxicity, endocrinopathy, dermatitis, pancreatitis and nephritis. Additional important potential risks include infusion-related reactions, hypersensitivity, anaphylaxis or serious allergic reactions, serious infections, and immune complex disease.

AEs that have occurred in durvalumab monotherapy trials and have been assessed to have at least a reasonable possibility of a causal relationship to durvalumab include:

- Very common (> 10/100)
 Diarrhea
- Common (> 1/100 and <10/100)
 - ALT increased
 - AST increased
 - Pneumonitis
- Uncommon (> 1/1,000 to <1/100)
 - o Colitis

The majority of diarrhea, ALT increased, AST increased, and pneumonitis events were reported to be mild to moderate in severity (CTCAE Grades 1/2), while for colitis the majority of events were reported to be moderate to severe (Grades 2/3). Please also refer to the Investigator's Brochure (IB).

7.1.2 Adverse Event List for Tremelimumab

Immune-mediated reactions, also considered to be adverse events of special interest or immune related adverse events (irAEs), are important risks of immune checkpoint inhibitors such as tremelimumab that can result in an inflammatory response in any organ or tissue including the liver, gastrointestinal tract, thyroid glands, pancreas, skin, nervous system, hematopoietic system, respiratory tract, kidney, and adrenal glands.

Potential immune-mediated reactions associated with tremelimumab include the following:

- Gastrointestinal events including colitis, intestinal perforation, abdominal pain, dehydration, nausea and vomiting, and decreased appetite (anorexia)
- Dermatitis including urticaria, skin exfoliation, and dry skin
- Endocrinopathies including hypophysitis, adrenal insufficiency, and hyper- and hypothyroidism
- Hepatitis including autoimmune hepatitis, and increased serum ALT and AST
- Pancreatitis including autoimmune pancreatitis, and lipase and amylase elevation
- Respiratory tract events including pneumonitis and interstitial lung disease (ILD)
- Nervous system events including encephalitis, peripheral motor and sensory neuropathies, Guillain-Barre and myasthenia gravis (the latter reported with combination of tremelimumab and durvalumab)
- Cytopenias including thrombocytopenia, anemia and neutropenia

Additional risks that are common to any immunoglobulin include infusion-related reactions, anaphylaxis, and serious acute IgE-mediated allergic reactions. These reactions may occur, may be severe, and may result in death.

Other potential risks identified with tremelimumab include headache, fatigue, and pyrexia. Please also refer to the IB.

7.1.3 Adverse Event List for Durvalumab and Tremelimumab Combined

Common (>10 % of subjects) treatment-related AEs of any grade occurring among subjects treated with the combination of durvalumab and tremelimumab include:

- Diarrhea
- Fatigue
- Increased amylase and pruritus
- Rash
- Colitis
- Increased lipase

7.2 Definition of Adverse Events

The International Conference on Harmonisation (ICH) Guideline for Good Clinical Practice (GCP) E6(R1) defines an adverse event (AE) as:

Any untoward medical occurrence in a patient or clinical investigation subject administered a pharmaceutical product and which does not necessarily have a causal relationship with this treatment. An AE can therefore be any unfavorable and unintended sign (including an abnormal laboratory finding), symptom, or disease temporally associated with the use of a medicinal product, whether or not considered related to the medicinal product.

An AE includes but is not limited to any clinically significant worsening of a subject's pre-

existing condition. The term disease progression should not be reported as an AE or serious adverse event (SAE), however, medically significant individual events and/or laboratory abnormalities associated with disease progression (see definition of disease progression below) that fulfill the AE or SAE definition should be reported. An abnormal laboratory finding (including ECG finding) that requires medical intervention by the investigator, or a finding judged by the investigator as medically significant should be reported as an AE. If clinical sequelae are associated with a laboratory abnormality, the diagnosis or medical condition should be reported (e.g., renal failure, hematuria) not the laboratory abnormality (e.g., elevated creatinine, urine red blood cell increased).

AEs may be treatment emergent (i.e., occurring after initial receipt of investigational product) or non-treatment emergent. A non-treatment-emergent AE is any new sign or symptom, disease, or other untoward medical event that begins after written informed consent has been obtained but before the subject has received investigational product.

Elective treatment or surgery or preplanned treatment or surgery (that was scheduled prior to the subject being enrolled into the study) for a documented pre-existing condition that did not worsen from baseline is not considered an AE (serious or non-serious). An untoward medical event occurring during the prescheduled elective procedure or routinely scheduled treatment should be recorded as an AE or SAE.

Adverse Events Associated with Disease Progression

Disease progression can be considered as a worsening of a subject's condition attributable to the disease for which the investigational product is being studied. It may be an increase in the severity of the disease under study and/or increases in the symptoms of the disease. The development of a new metastasis or progression of existing metastasis related to the primary cancer under study should not be considered an AE. Death clearly resulting from disease progression should NOT be reported as an SAE (see reporting guidelines in Section 7.4).

New Cancers

The development of a new cancer should be regarded as an SAE. New cancers are those that are not the primary reason for the administration of the investigational product and have been identified after the subject's inclusion in the study. New metastatic lesion(s) of the subject's known cancer should NOT be reported as a new cancer.

7.3 **Adverse Event Characteristics**

• **CTCAE term (AE description) and grade:** The descriptions and grading scales found in the revised NCI Common Terminology Criteria for Adverse Events (CTCAE) version 4.03 will be utilized for AE reporting. All appropriate treatment areas should have access to a copy of the CTCAE version 4.03. A copy of the CTCAE version 4.03 can be downloaded from the CTEP web site

http://ctep.cancer.gov/protocolDevelopment/electronic applications/ctc.htm.

- For expedited reporting purposes only:
 - AEs for the agent(s) that are listed above should be reported only if the adverse event varies in nature, intensity or frequency from the expected toxicity information which is provided.
- **Attribution** of the AE:
 - Definite The AE *is clearly related* to the study treatment.
 - Probable The AE is likely related to the study treatment.
 - Possible The AE *may be related* to the study treatment.
 - Unlikely The AE is doubtfully related to the study treatment.
 - Unrelated The AE is clearly NOT related to the study treatment.

